9.1.3 Duration of Response (DOR)

DOR is defined as the time from the first tumor assessment that supports the patient's objective disease response (CR, PR) to the time of disease progression or death due to any cause. DOR will be computed only for patients who have been identified as responders during the study.

9.1.4 Overall Survival (OS)

OS is defined as the time from first dose of study drug until date of death due to any cause. Patients without documentation of death at the time of analysis will be censored as of the date the patient was last known to be alive. For patients who are lost to follow up, the last visit in the database or last contact date when the patient is documented to be alive will be used as the last known date alive.

9.1.5 Change from Baseline in PSA

PSA testing was conducted at local laboratory facilities at each site and entered into EDC as per the protocol schedule.

By-patient data listings will be provided reporting the change from baseline over time for all patients with non-missing data at baseline, including the maximum percent change from baseline.

9.1.6 Duration of Disease Control (DODC)

DODC is defined as the time from the first tumor assessment that supports the patient's disease control (CR, PR, SD) to the time of disease progression or death due to any cause. DODC will be computed only for patients who have been identified as having disease control during the study.

10 SAFETY

All safety analyses will be based on the Safety Population.

10.1 Study Drug Exposure and Compliance

A summary of HPN424 study drug exposure and compliance will be provided. The number of cycles of administration (of any dose within the cycle) of HPN424 will be reported as continuous and categorical outcomes (e.g., by cycle). Total infusions, total dose received, total dose planned, and treatment duration in weeks will be summarized. Total number of dose modifications and reasons for modification will be summarized.

10.2 Adverse Events

Verbatim AE terms will be coded based using the Medical Dictionary for Regulatory Activities (MedDRA) Version 24.0 for reporting by System Organ Class (SOC) and Preferred Term (PT). The MedDRA version number will be reported in footnotes on each AE table and described in the study report.

The severity of AEs is graded by the Investigator according to the NCI CTCAE version 5.0, with the exception of CRS, which was graded by ASTCT criteria.

Treatment-emergent adverse events (TEAEs) are defined as all events that occur or worsen in severity during or after the first HPN424 study drug administration through 28 days after the last dose of study drug. In addition, any event that occurs after this time period is reported as a TEAE if the event is assessed by the investigator as related to study drug.

An overall summary of TEAEs will be provided that includes the patient incidences (numbers and percentages) by cohort and overall of the following categories of events:

- TEAEs
- TEAEs related to study drug
- NCI CTCAE Grade 3 or higher TEAEs
- NCI CTCAE Grade 3 or higher TEAEs related to study drug
- Treatment-emergent SAEs
- Treatment-emergent SAEs related to study drug
- Dose limiting toxicities (DLTs)
- CRS or IRR TEAEs
- TEAEs that lead to study drug discontinuation
- TEAEs related to study drug that lead to study drug discontinuation
- TEAEs that lead to dose reduction or interruption
- TEAEs related to study drug that lead to dose reduction or interruption
- Fatal TEAEs
- Fatal TEAEs related to study drug

The patient incidence by cohort of each of the above categories of TEAEs will be summarized separately by SOC and PT. Multiple TEAEs will be counted once per patient within each SOC and each PT. For TEAE summaries, multiple TEAEs will be counted once per patient at the

maximum severity NCI CTCAE grade reported within each SOC and each PT. Tables will be sorted by SOC and PT frequency in descending order of overall incidence.

An additional patient incidence summary will be provided sorted by PT showing TEAEs with an overall patient incidence rate > 10%.

Non treatment-emergent adverse events will be included only in the by-patient data listings.

10.3 Cytokine Release Syndrome (CRS) and Infusion Related Reactions (IRR) AEs

Cytokine Release Syndrome (CRS) and Infusion Related Reactions (IRR) are considered adverse events of clinical interest. CRS symptoms were collected in a separate module in EDC to more accurately capture timing and severity of each symptom associated with CRS.

Unlike all other AEs, CRS was graded according to ASTCT criteria ([Lee, 2019](#)), a more detailed grading system designed for CAR-T cell and immune effector cell therapies. Prior to October 2021 (protocol Amendment 6), CRS was graded according to [Lee 2014](#) criteria. The primary difference between the two grading systems is the inclusion (Lee 2014) vs exclusion (ASTCT) of organ toxicity in grading CRS. ASTCT focuses on the extent of hypotension and hypoxia, and organ toxicity is graded separately. Legacy CRS grades were re-assessed by the site and updated in EDC to ASTCT grade as required.

For CRS only, all AE summary tables will report the ASTCT grade rather than NCI CTCAE grading. Tables will be footnoted to ensure clarity:

- All adverse events are graded according to NCI-CTCAE v5.0 except Cytokine Release Syndrome, which is graded according to ASTCT

In addition to the described AE tables and to ensure they are captured consistently, CRS symptoms will be summarized separately showing incidence of symptoms from the CRS symptom page.

10.4 Deaths

The numbers and percentages of patients who died overall (ie, including survival follow-up and publicly available data for patients lost to follow-up) and within 28 days of last dose of study drug will be summarized. The summary will also include the reported causes of death.

10.5 Safety Laboratory Assessments

Routine hematology, serum chemistry, and coagulation parameters will be converted from the institution's local laboratory results and reported based on the International System of Units (SI). Textbook normal ranges will be used when local laboratory ranges are not available. Safety laboratory reporting specifications are described in Section [13.3](#). NCI CTCAE laboratory toxicity grading is described in Section [13.4](#). Note that toxicity grading is based exclusively on quantitative laboratory results and does not include clinical interpretation. When CTCAE grades have overlapping laboratory ranges and are differentiated based on clinical assessment, the higher grade is assigned. All tables and listings that report safety laboratory grades should contain the footnote:

See Statistical Analysis Plan Sections [13.3](#) and [13.4](#) for details regarding laboratory grading

The following summaries of hematology, and serum chemistry, and coagulation parameters will be provided by treatment group and overall, for all NCI-CTCAE graded parameters:

- Shifts from baseline NCI CTCAE grade to maximum post-baseline NCI CTCAE grade

Urinalysis data will be provided in a by-patient data listing only.

A by-patient data listing of patients who have laboratory values that meet Hy's Law criteria will be provided.

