6.23.6 Other Experiences Immediately Reportable to the Sponsor

The following immediately reportable experiences should always be assessed for seriousness criteria first, and if those criteria are not met, then they must be entered on the AE CRF and SAE form and reported within 24 hours of first knowledge of the event by study personnel, using the expedited reporting procedures described in [Section 6.23.7](#).

- ALT or AST with a 3-fold or greater elevation above the upper limit of normal (ULN) in addition to an elevation of serum total bilirubin greater than two times the ULN, with no other identifiable etiology
- Liver enzyme (ALT or AST) value greater than or equal to 5 times the ULN

In addition, if a patient's partner becomes pregnant any time after the first dose of study drug through the end of the required contraception period, the pregnancy must be immediately reported on a Pregnancy Report Form to the Sponsor or its designee. The pregnancy must be followed until the outcome of the pregnancy or for a minimum of 6 months following the birth of the child. Follow-up information regarding the outcome of the pregnancy and any postnatal sequelae must be provided to the Sponsor.

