7.2 Definitions of Study Day, Durations, Baseline, and Post-Baseline Changes

Study day will be based on the date of administration of the first dose of HPN424 study treatment. Date calculations for any duration outcomes will be defined as follows:

- date of interest – first dose date + 1, when the date of interest is on or after the first dose date
- date of interest – first dose date, when the date of interest is before the first dose date

Study Day 1 is defined as the day the first dose of HPN424 study treatment is administered.

Duration outcomes will generally be reported in days. When necessary to convert to weeks, the duration in days will be divided by 7. When necessary to convert to months, the duration in days will be divided by 30.4375. When necessary to convert to years, the duration in days will be divided by 365.25.

Baseline will be based on the last non-missing value collected before or on the date (and time, if applicable) of the first dose of HPN424 study treatment. Post-baseline values will be those collected after the first dose of study treatment.

Change from baseline is defined as: post-baseline value – baseline value.

Percentage change from baseline is defined as:

$[(\text{post-baseline value} - \text{baseline value}) / \text{baseline value}] \times 100\%$

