14.3.2.14	Summary of Treatment Emergent Adverse Events Related to HPN424 That Lead to HPN424 Dose Modifications by System Organ Class and Preferred Term
14.3.2.15	Summary of Dose Limiting Toxicity (DLT) Adverse Events by System Organ Class and Preferred Term
14.3.2.16	Summary of CRS Signs and Symptoms by Preferred Term (From CRS Symptom CRF)
14.3.2.17	Summary of IRR Signs and Symptoms by Preferred Term (From CRS Symptom CRF)

Table Number	Description
14.3.3	Summary of Deaths
14.3.4.1	Safety Laboratory Assessment Shift Table – Serum Chemistry Change from Baseline to Maximum Post-Baseline NCI CTCAE Grade
14.3.4.2	Safety Laboratory Assessment Shift Table – Hematology Change from Baseline to Maximum Post-Baseline NCI CTCAE Grade
14.3.4.3	Safety Laboratory Assessment Shift Table – Coagulation Change from Baseline to Maximum Post-Baseline NCI CTCAE Grade
14.3.4.4	Safety Laboratory Assessment Summary of Patients with Post-Baseline NCI CTCAE Grade 3 or Higher
14.3.5	Summary of 12-Lead Electrocardiogram Abnormalities and Potential QTcF Interval Prolongation
14.3.6	Study Drug Exposure and Compliance

Table of Contents - Listings

Listing Number	Description
16.2.1	Patient Disposition
16.2.2	Patient Enrollment and Eligibility (Inclusion / Exclusion)
16.2.3	Protocol Deviations
16.2.4.1	Demographics
16.2.4.2	Prostate Cancer Medical History
16.2.4.3	Prior Anticancer Therapy
16.2.4.4	Prior Radiation Therapy
16.2.4.5	Prior Prostate Cancer-related Surgery
16.2.4.6	Medical History
16.2.5.1	HPN424 Administration
16.2.5.2	HPN424 Infusion Interruptions
16.2.5.3	Hospital Admission
16.2.6.1	Overall Efficacy Endpoints
16.2.6.2	Radiographic Scans
16.2.6.3	Target Lesions
16.2.6.4	Non-target Lesions
16.2.6.5	New Lesions
16.2.6.6	Bone Scan Assessment
16.2.6.7	Overall Disease Assessment

Listing Number	Description
16.2.6.8	PSA Results
16.2.7.1	Adverse Events
16.2.7.2	Serious Adverse Events
16.2.7.3	Dose-limiting Toxicities
16.2.7.4	Adverse Events Leading to Treatment Discontinuation
16.2.7.5	Adverse Events Leading to HPN424 Dose Modifications
16.2.7.6	Fatal Adverse Events
16.2.7.7	Cytokine Release Syndrome / Infusion Related Reactions Symptoms
16.2.7.8	Deaths
16.2.8.1	Laboratory Results: Hematology
16.2.8.2	Laboratory Results: Chemistry and Testosterone
16.2.8.3	Laboratory Results: Coagulation
16.2.8.4	Laboratory Results: Urinalysis
16.2.8.5	NCI CTCAE Grade 3 or Higher Laboratory Results
16.2.8.6	Patients who had laboratory values that Meet Criteria for Hy's Law

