13.4 NCI CTCAE v5.0 Laboratory Toxicity Grading

Lab Test (CTCAE Term)	Increase / Decrease	Grade 1	Grade 2	Grade 3	Grade 4
Hematology					
WBC (leukocytosis)	Increase	---	---	>100,000 /mm3	---
WBC (decreased)	Decrease	<LLN – 3000 /mm3 <LLN – 3.0 10^9/L	<3000 – 2000 /mm3 <3.0 – 2.0 10^9/L	<2000 – 1000 /mm3 <2.0 – 1.0 10^9/L	<1000 /mm3 <1.0 10^9/L
ANC (decreased)	Decrease	<LLN – 1500 /mm3 <LLN – 1.5 10^9/L	<1500 – 1000 /mm3 <1.5 – 1.0 10^9/L	<1000 – 500 /mm3 <1.0 – 0.5 10^9/L	<500 /mm3 <0.5 10^9/L
Lymphocytes (increased)	Increase	---	>4000 – 20,000 /mm3	>20,000 /mm3	---
Lymphocytes (decreased)	Decrease	<LLN – 800 /mm3 <LLN – 0.8 10^9/L	<800 – 500 /mm3 <0.8 – 0.5 10^9/L	<500 – 200 /mm3 <0.5 – 0.2 10^9/L	<200 /mm3 <0.2 10^9/L
Eosinophils (eosinophilia)	Increase	> ULN and > BL	---	---	---
Hemoglobin (anemia)	Decrease	<LLN – 10 g/dL <LLN – 6.2 mmol/L <LLN – 100 g/L	<10 – 8 g/dL <6.2 – 4.9 mmol/L <100 – 80 g/L	<8 g/dL <4.9 mmol/L <80 g/L	---
Hemoglobin (increased) [1]	Increase	>0 – 2 g/dL above ULN or above BL if BL is > ULN	>2 – 4 g/dL above ULN or above BL if BL is > ULN	>4 g/dL above ULN or above BL if BL is > ULN	---
Platelets (decreased)	Decrease	<LLN – 75,000 /mm3 <LLN – 75.0 10^9/L	<75,000 – 50,000 /mm3 <75.0 – 50.0 10^9/L	<50,000 – 25,000 /mm3 <50.0 – 25.0 10^9/L	<25,000 /mm3 <25.0 10^9/L
Coagulation					
APTT (prolonged)	Increase	>ULN – 1.5x ULN	>1.5 – 2.5x ULN	>2.5x ULN	---
INR (increased)	Increase	>1.2 – 1.5	>1.5 – 2.5	>2.5	---
Chemistry					
ALT (increased)	Increase	>ULN – 3.0x ULN if BL was normal 1.5 – 3.0x BL if BL was abnormal	>3.0 – 5.0x ULN if BL was normal >3.0 – 5.0x BL if BL was abnormal	>5.0 – 20.0x ULN if BL was normal >5 – 20.0x BL if BL was abnormal	>20.0x ULN if BL was normal >20.0x BL if BL was abnormal

Lab Test (CTCAE Term)	Increase / Decrease	Grade 1	Grade 2	Grade 3	Grade 4
AST (increased)	Increase	>ULN – 3.0x ULN if BL was normal 1.5 – 3.0x BL if BL was abnormal	>3.0 – 5.0x ULN if BL was normal >3.0 – 5.0x BL if BL was abnormal	>5.0 – 20.0x ULN if BL was normal >5 – 20.0x BL if BL was abnormal	>20x ULN if BL was normal >20.0x BL if BL was abnormal
ALK PHOS (increased)	Increase	>ULN – 2.5x ULN if BL was normal 2.0 – 2.5x BL if BL was abnormal	>2.5 – 5.0x ULN if BL was normal >2.5 – 5.0x BL if BL was abnormal	>5.0 – 20.0x ULN if BL was normal >5.0 – 20.0x BL if BL was abnormal	>20.0x ULN if BL was normal >20.0x BL if BL was abnormal
LDH (increased)	Increase	>ULN	---	---	---

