Total Bilirubin (increased)	Increase	>ULN – 1.5x ULN if BL was normal >1.0 – 1.5x BL if BL was abnormal	>1.5 – 3.0x ULN if BL was normal >1.5 – 3.0x BL if BL was abnormal	>3.0 – 10.0x ULN if BL was normal >3.0 – 10.0x BL if BL was abnormal	>10x ULN if BL was normal >10.0x BL if BL was abnormal
Albumin (hypoalbuminemia)	Decrease	<LLN – 3.0 g/dL <LLN – 30 g/L	<3 – 2 g/dL <30 – 20 g/L	<2 g/dL <20 g/L	---
Creatinine (increased)	Increase	>ULN – 1.5x ULN	>1.5 – 3.0x ULN or >1.5 – 3.0x BL	>3.0 – 6.0x ULN or >3.0x BL – 6.0x ULN	>6.0x ULN
Glucose (hypoglycemia)	Decrease	<LLN – 55 mg/dL <LLN – 3.0 mmol/L	<55 – 40 mg/dL <3.0 – 2.2 mmol/L	<40 – 30 mg/dL <2.2 – 1.7 mmol/L	<30 mg/dL <1.7 mmol/L
Lipase (increased)	Increase	>ULN – 1.5x ULN	>1.5 – 2.0x ULN	>2.0 – 5.0x ULN	>5.0x ULN
Amylase (increased)	Increase	>ULN – 1.5x ULN	>1.5 – 2.0x ULN	>2.0 – 5.0x ULN	>5.0x ULN
Corrected Calcium (hypercalcemia) [2]	Increase	>ULN – 11.5 mg/dL >ULN – 2.9 mmol/L	>11.5 – 12.5 mg/dL >2.9 – 3.1 mmol/L	>12.5 – 13.5 mg/dL >3.1 – 3.4 mmol/L	>13.5 mg/dL >3.4 mmol/L
Corrected Calcium (hypocalcemia) [2]	Decrease	<LLN – 8.0 mg/dL <LLN – 2.0 mmol/L	<8.0 – 7.0 mg/dL <2.0 – 1.75 mmol/L	<7.0 – 6.0 mg/dL <1.75 – 1.5 mmol/L	<6.0 mg/dL <1.5 mmol/L
Potassium (hyperkalemia)	Increase	>ULN – 5.5 mmol/L	>5.5 – 6.0 mmol/L	>6.0 – 7.0 mmol/L	>7.0 mmol/L

Lab Test (CTCAE Term)	Increase / Decrease	Grade 1	Grade 2	Grade 3	Grade 4
Potassium (hypokalemia)	Decrease	--	<LLN – 3.0 mmol/L	<3.0 – 2.5 mmol/L	<2.5 mmol/L
Magnesium (hypermagnesemia)	Increase	>ULN – 3 mg/dL >ULN – 1.23 mmol/L	---	>3 – 8 mg/dL >1.23 – 3.30 mmol/L	>8.0 mg/dL >3.30 mmol/L
Magnesium (hypomagnesemia)	Decrease	<LLN – 1.2 mg/dL <LLN – 0.5 mmol/L	<1.2 – 0.9 mg/dL <0.5 – 0.4 mmol/L	<0.9 – 0.7 mg/dL <0.4 – 0.3 mmol/L	<0.7 mg/dL <0.3 mmol/L
Sodium (hypernatremia)	Increase	>ULN – 150 mmol/L	>150 – 155 mmol/L	>155 – 160 mmol/L	>160 mmol/L
Sodium (hyponatremia)	Decrease	<LLN – 130 mmol/L	---	120 - <130 mmol/L	<120 mmol/L
Uric Acid (increased)	Increase	---	---	> ULN	---

[1] For hemoglobin grading, in order to maintain the intention of CTCAE v4.03, the assumption is made that grading for increased levels are compared to ULN if baseline result is within normal range, or above baseline if baseline is above ULN.

[2] Serum calcium is corrected for albumin to assign CTCAE Grade; corrected calcium is derived as follows:

$$\text{corrected-CA (mmol/L)} = \text{serum-CA (mmol/L)} + 0.020 * (40 - \text{albumin (g/L)})$$

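### The liver-test shift tables have no workable baseline axis, because SAP 13.4 grades abnormal-baseline patients against their own baseline, and no planned table summarises absolute elevations

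*SAP*

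**What the plan says.** SAP 10.5 asks, for all CTCAE-graded hematology, chemistry and coagulation tests, for "Shifts from baseline NCI CTCAE grade to maximum post-baseline NCI CTCAE grade". Grades come from the numbers alone: "Note that toxicity grading is based exclusively on quantitative laboratory results and does not include clinical interpretation". SAP 7.2 says which value is the baseline ("Baseline will be based on the last non-missing value collected before or on the date (and time, if applicable) of the first dose") but not how to grade it.

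SAP 13.4 has two branches for ALT, AST, ALP and total bilirubin. If baseline was normal, the cut-points are multiples of ULN. If it was abnormal, they are multiples of baseline (BL). On the second branch Grade 1 is "1.5 – 3.0x BL if BL was abnormal" for ALT and AST, "2.0 – 2.5x BL if BL was abnormal" for ALP and ">1.0 – 1.5x BL if BL was abnormal" for bilirubin. Grade 3 starts above 5 x BL for ALT, AST and ALP, and above 3 x BL for bilirubin.

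SAP 13.1 lists Table 14.3.4.4, "Safety Laboratory Assessment Summary of Patients with Post-Baseline NCI CTCAE Grade 3 or Higher". Protocol 6.23.6 uses an absolute scale whatever the baseline; one of its immediately reportable findings is "Liver enzyme (ALT or AST) value greater than or equal to 5 times the ULN". Protocol 4.2 admits ALT and AST up to 2.5 x ULN and bilirubin up to 1.5 x ULN (5 mg/dL in Gilbert syndrome), and sets no ALP limit.

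**The concern.** A shift table is read by comparing its rows (grade at entry) with its columns (worst grade on treatment). If the rows cannot separate a patient who entered with normal liver tests from one who entered at 2.5 x ULN, the table does not show a shift. If rows and columns use different scales, it shows shifts that did not happen.

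The synoptic report is focused on safety, and laboratory abnormalities remain an active secondary endpoint. Protocol 5.4 names raised liver enzymes among the primary anticipated risks, and 5.4.3 reports that Grade 3-4 transaminitis has already been seen with HPN424. These are the main laboratory tables for a known risk. ALP deserves particular attention: it has no entry limit, and protocol 1.2 puts bone metastases at about 90% of patients with castrate-resistant disease.

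**Working it through.** The plan states no figure on this point to reproduce. The check applies the SAP 13.4 bands literally. All values are in multiples of ULN unless marked.

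**1. Grade of the baseline value on the SAP 13.4 branches.**
- Normal baseline: at or below ULN, so Grade 0.
- Abnormal baseline: ratio = BL ÷ BL = 1.0. The Grade 1 floors are 1.5 (ALT/AST), 2.0 (ALP) and more than 1.0 (bilirubin). 1.0 reaches none of them, so Grade 0.
- Running baselines from 0.01 to 30 x ULN through the bands gives 0 as the only baseline grade for all four tests. Each shift table collapses to one row.

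**2. The alternative: grade baseline on ULN and later values by SAP 13.4.** ALT of 2.4 at baseline and 2.4 throughout:
- Baseline: 2.4 lies above ULN and not above 3.0 x ULN, so Grade 1.
- Post-baseline: 2.4 ÷ 2.4 = 1.0, below 1.5, so Grade 0.
- The table prints Grade 1 to Grade 0 for a patient whose ALT did not change.

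**3. Where Grade 3 starts for an abnormal baseline.** Threshold = 5 x BL (ALT, AST, ALP) or 3 x BL (bilirubin).

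| Test | Baseline | Grade 3 above | If baseline normal |
|---|---|---|---|
| ALT/AST | 1.5 | 5 x 1.5 = 7.5 | 5 |
| ALT/AST | 2.0 | 5 x 2.0 = 10 | 5 |
| ALT/AST | 2.5 | 5 x 2.5 = 12.5 | 5 |
| ALP | 3 | 5 x 3 = 15 | 5 |
| ALP | 6 | 5 x 6 = 30 | 5 |
| Bilirubin | 1.5 | 3 x 1.5 = 4.5 | 3 |

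**4. Example patients, graded by SAP 13.4 and by the same cut-points on ULN at both times.**

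| Test | Baseline to maximum | Maximum ÷ BL | SAP 13.4 | ULN at both times |
|---|---|---|---|---|
| ALT | 2.5 to 12 | 4.8 | 0 to 2 | 1 to 3 |
| ALT | 2.0 to 9 | 4.5 | 0 to 2 | 1 to 3 |
| ALP | 3 to 14 | 4.67 | 0 to 2 | 2 to 3 |
| ALP | 6 to 11 | 1.83 | 0 to 0 | 3 to 3 |
| Bilirubin | 1.5 to 4.4 | 2.93 | 0 to 2 | 1 to 3 |

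There is also a jump at the boundary. A baseline of 1.00 rising to 5.1 is Grade 3; a baseline of 1.01 rising to 5.04 (ratio 4.99) is Grade 2.

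**5. Who changes status in Table 14.3.4.4.** For ALT, AST and ALP with a baseline above ULN, only patients whose maximum is above 5 x ULN but not above 5 x BL. For bilirubin the corresponding limits are 3 x ULN and 3 x BL. This is a subset of the patients with raised baselines.

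**6. Abnormal is not defined as high.** SAP 13.3 gives bilirubin a textbook range of 5.1-20.5 µmol/L. A baseline of 4.0 is abnormal because it is low. A rise to 12.5, inside the range, gives 12.5 ÷ 4.0 = 3.125, which is Grade 3. Misplacement can therefore run in either direction.

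**The case against.** The strongest reply is that the SAP does what the protocol asks. Protocol 10.7 prescribes laboratory shift tables by CTCAE v5.0 grade, SAP 13.4 is headed as that grading, and Table 14.3.4.4 is titled by it. A reader might infer that this table wrongly omits patients. The documents do not support that: under SAP 13.4 it counts what its title says. What it leaves out is absolute level, and the remedy for that is a supplement.

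A reader might also take it as settled that every baseline grade will be 0. The SAP never says so. The branches are worded as though for post-baseline values, and a programmer might grade baseline on ULN. That choice does not rescue the table, as step 2 shows.

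Nor are reportable values lost to the study report. Protocol 6.23.6 requires ALT or AST of at least 5 x ULN to be entered on the AE form even when not serious, and SAP 5.5 reports adverse events from that database, so they should reach the AE tables, though the AE grade might itself be baseline-adjusted. Listing 16.2.8.2 shows all chemistry values, Listing 16.2.8.6 covers Hy's Law, and SAP 8.4 summarises baseline ALP.

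These mitigations are real but partial. The listings are by patient, the Hy's Law criterion is a joint one, and the baseline ALP summary is not linked to later values. Protocol 10.7 also promises a summary table for each laboratory parameter, which might have shown absolute levels, but the SAP's table list contains only grade-based laboratory tables.

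**Conclusion.** The point holds for the shift tables under either reading of the SAP: for the four liver tests the baseline axis is empty or is on a different scale from the post-baseline axis, and no other section resolves this. For Table 14.3.4.4 the point is narrower. The table matches its label, but at ALT/AST baselines of 1.5 to 2.5 x ULN it begins counting only above 7.5 to 12.5 x ULN, and no planned table summarises elevations on the protocol's own absolute scale.

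The number of patients affected cannot be given, because the documents contain no distribution of baseline liver tests. It would be wrong to equate it with the share of abnormal baselines; for the Grade 3+ table it is the subset in step 5. It would also be wrong to say the error is always an understatement, given step 6.

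This should be fixed, but it does not threaten the study's main conclusions. The analyses are descriptive with no p-values, Part 2 was never started, and the primary endpoint of DLTs does not use these tables. The conclusion rests on applying SAP 13.4 as written, which is the only grading rule the SAP gives.

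**What to change.** Keep the CTCAE shift tables and Table 14.3.4.4, since protocol 10.7 calls for CTCAE-based shifts. For ALT, AST, ALP and total bilirubin:

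- In SAP 13.4, define an abnormal baseline as one above ULN.
- Add a supplementary shift table in multiples of ULN at both baseline and worst post-baseline, with baseline-normal and baseline-abnormal patients shown separately.
- Add a summary of the maximum post-baseline value regardless of baseline: ALT/AST at least 3, at least 5, above 10 and above 20 x ULN; bilirubin above 2 x ULN. The at-least signs matter. Protocol 6.23.6 includes values of exactly 3 and 5 x ULN, and strict thresholds would leave them out.
- Footnote the CTCAE tables to say that grades for these tests are baseline-adjusted.

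The cost is some SAP wording and one extra liver table holding the two added displays. Some patients at or above 5 x ULN will carry no Grade 3 flag, which the footnote explains.
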